## DOCUMENT HISTORY

Document	Date of Issue	Overall Rationale
Amendment 2	17-MAY-2024	This amendment allows for the evaluation of more conservative dose regimens (Dose Regimens 2 and 3) even if Dose Regimen 1 is generally well tolerated.
Amendment 1	29-FEB-2024	This amendment was primarily created to include assessments to monitor treatment-emergent mania and depression and to add participant-level and study-level stopping rules.
Original Protocol	12-JAN-2024	Not applicable

## PROTOCOL AMENDMENT SUMMARY OF CHANGES

### Amendment: 01

#### Overall Rationale for the Amendment:

This amendment allows for the evaluation of more conservative dose regimens (Dose Regimen 2 and Dose Regimen 3) even if Dose Regimen 1 is generally well tolerated.

#### Summary of Changes Table

Section Number and Name	Description of Change	Brief Rationale
Primary Reason for Amendment		
Section 4.1 Overall Design	The overall design allows for the evaluation of more conservative Dose Regimens, even if the more rapid titration or no titration is generally well tolerated.	To further inform optimal dose selection for Phase 3 trials.
Additional Changes		
Section 1.1 Synopsis	Increase sample size from 32 to 48	Allow for the enrollment of more conservative Dose Regimens to further inform on dose selection for Phase 3
Section 4.2 Scientific Rationale for Study Design	Updated to include optimizing tolerability to explore a regimen with a titration.	To further inform optimal dose selection for Phase 3
Section 8.10.6 Study Design/Dosing/Procedures Modifications Permitted Within Protocol Parameters	Allow for a panel to be repeated at the same Dose Regimen and allow for a more conservative non-protocol-specified Dose Regimen to be evaluated.	Allow for the evaluation of additional more conservative Dose Regimens to further inform on dose selection for Phase 3.

## 1 PROTOCOL SUMMARY

### 1.1 Synopsis

**Protocol Title:** A Multiple Dose Clinical Study to Evaluate the Safety, Tolerability and Pharmacokinetics of MK-8189 in Participants with Bipolar I Disorder

**Short Title:** MK-8189 Study in Bipolar I Participants

**Acronym:** N/A

### Hypotheses, Objectives, and Endpoints:

Hypotheses are aligned with objectives in the Objectives and Endpoints table.

The following objectives will be evaluated in male and female participants with bipolar I disorder:

Primary Objective	Primary Endpoint
To evaluate the safety and tolerability of multiple doses of MK-8189 in participants with bipolar I disorder, manic or mixed features	Adverse events Adverse experiences leading to discontinuation of study intervention
Secondary Objectives	Secondary Endpoints
Not applicable	Not applicable

**Overall Design:**

Study Phase	Phase 1
Primary Purpose	Treatment
Indication	Bipolar disorder
Population	Participants with Bipolar I Disorder
Study Type	Interventional
Intervention Model	Sequential This is a multi site study.
Type of Control	Placebo
Study Blinding	Double-blind
Blinding Roles	Participants or Subjects Investigator
Estimated Duration of Study	The Sponsor estimates that the study will require approximately 5.5 months from the time the first participant (or their legally acceptable representative) provides documented informed consent until the last participant's last study-related contact.

**Number of Participants:**

Up to approximately 48 adult participants with bipolar I disorder will be randomized such that 16 evaluable participants, in one dose regimen, complete the study as described in Section 9.

### Intervention Groups and Duration:

Arm Name	Intervention Name	Unit Dose Strength(s)	Dosage Level(s)	Route of Administration	Regimen/ Treatment Period/ Vaccination Regimen	Use
Active	MK-8189	4 mg 12 mg	All dose levels	Oral	Dose Regimens 1, 2 and 3	Test Product
Placebo	Placebo	0 mg	All dose levels	Oral	Dose Regimens 1, 2 and 3	Placebo

Total Number of Intervention Groups/Arms	2
Duration of Participation	Each participant will participate in the study for approximately 10 weeks from the time the participant provides documented informed consent through the final contact. After a screening phase of up to 42 days each participant will receive assigned intervention for approximately 14 days. After the end of treatment each participant will be followed for 14 days.

### Study Governance Committees:

Executive Oversight Committee	No
External Data Monitoring Committee	No
Clinical Adjudication Committee	No

Study governance considerations are outlined in Appendix 1.

[figure not shown]
## Study Accepts Healthy Participants: No

A list of abbreviations is in Appendix 12.

### 1.2 Schema

The study design is depicted in [Figure 1](#).

Figure 1 Study Schema

### 1.3 Schedule of Activities

Panels A, B, C																					
Study Period:	Screening/ Rescreening a	Washout	Intervention																Poststudy	Notes	
Scheduled Day	Up to -42	-5 to -1	Day 1 Predose	1	2	3	4	5, 6	7	8	9	10	11	12	13	14	15, 16	17	+14 post last dose		
MK-8189/Placebo Administration				X	X	X	X	X	X	X	X	X	X	X	X	X				Section 8.1.8	
Standard Meals b				X						X						X				Sections 5.3.1, 5.3.2.1	
Domiciling c		X	--	-	-	-	-	-	-	-	-	-	-	-	-	-	-	X		Section 8.1.11 Participants will be domiciled minimally from Day -1 through Day 14 72 hours procedures are complete.	
Safety Procedures																					
Full physical examination	X		X															X	X	Section 8.3.1 Day 1 predose: up to 24 hours prior to dosing	
Height	X																				
Weight	X																	X		BMI to be taken only at Screening	
Full Neurological Exam	X		X																	Section 10.11.1	
Targeted Neurological Exam										X						X			X	Section 10.11.2	
Resting VS (HR, BP)	X		X			X		X		X					X		X	X		Section 8.3.2 HR and BP will be taken in triplicate. Intervention days: predose. Day 17: approximately the same time as Day 14	

Panels A, B, C																				
Study Period:	Screening/ Rescreening a	Washout	Intervention															Poststudy	Notes	
Scheduled Day	Up to -42	-5 to -1	Day 1 Predose	1	2	3	4	5, 6	7	8	9	10	11	12	13	14	15, 16	17	+14 post last dose	
Orthostatic VS	X		X			X			X		X				X		X	X	Section 8.3.2 Intervention days: predose. Day 17: approximately the same time as Day 14	
Resting VS (RR, T)	X		X			X					X						X	X	Section 8.3.2 Intervention days: predose Day 17: approximately the same time as Day 14	
12-lead ECG	X		X			X			X		X				X		X	X	Section 8.3.3 ECGs will be taken in triplicate. Intervention days: predose. Day 17: approximately the same time as Day 14	
Serum hCG (POCBP only)	X																	X	Sections 5.1, 8.3.5, 10.2, 10.5.	
Urine or Serum hCG Pregnancy Test d (POCBP only)			X																Sections 5.1, 8.3.5, 10.2, 10.5 Day 1 predose: up to 24h (urine) or 72h (serum) prior to dosing.	
Serum FSH (PONCBP only)	X																		Sections 10.2, 10.5	
HIV, hepatitis B and C screen (per site SOP)	X																		Section 10.2	
Drug screen (per site SOP)	X		X																Day 1 predose: up to 72h prior to dose. Additional drug screens are conducted per site SOP.	

Panels A, B, C																					
Study Period:	Screening/ Rescreening a	Washout	Intervention																Poststudy	Notes	
Scheduled Day	Up to -42	-5 to -1	Day 1 Predose	1	2	3	4	5, 6	7	8	9	10	11	12	13	14	15, 16	17	+14 post last dose		
Laboratory Safety (Hematology, Chemistry and Urinalysis)	X		X						X							X		X	X	Sections 8.3.4, 10.2 Day 1 predose: up to 72h prior to dose	
AE/SAE review	X	-----	-----	-	-	-	-	--	-	-	-	-	-	-	-	-	-----	-	X		
C-SSRS Baseline	X																			Section 8.3.6.1	
C-SSRS Since Last Assessment			X					X		X				X		X		X	X	Section 8.3.6.1 Day 1 predose: up to 24h prior to dose Intervention days: predose Day 17: approximately the same time as Day 14	
EPS Scales (BARS, AIMS, SAS)			X						X							X				Section 8.3.8 Day 1 predose: up to 24h prior to dose Intervention days: within 3 hours after dose.	
CGI-BP-S	X		X						X							X				Section 8.3.9 Day 1 predose: up to 24h prior to dose Day 7, 14: predose	
YMRS c	X		X						X							X				Section 8.3.9 Day 1 predose: up to 24h prior to dose Day 7, 14: predose	

Panels A, B, C																					
Study Period:		Screening/ Rescreening a	Washout	Intervention															Poststudy	Notes	
Scheduled Day		Up to -42	-5 to -1	Day 1 Predose	1	2	3	4	5, 6	7	8	9	10	11	12	13	14	15, 16	17	+14 post last dose	
HAM-D17 e	X		X							X								X		Section 8.3.9 Day 1 predose: up to 24h prior to dose Day 7, 14: predose	
Pharmacokinetics																					
Blood for Plasma MK-8189 and/or Metabolites Assay f					X	X					X	X						X	X	Section 8.6	
Biomarkers																					
Blood for Genetic Analysis				X																Section 8.8 The PGA sample should be obtained predose on Day 1 but may be collected at the next scheduled blood draw, if needed.	

AE=adverse event; AIMS = Abnormal Involuntary Movement Scale; BARS = Barnes Akathisia Rating Scale; CGI-BP-S: Clinical Global Impressions-Bipolar Version-Severity of Illness; C-SSRS=Columbia-Suicide Severity Rating Scale; EC=exclusion criteria; ECG=electrocardiogram; EPS = Extrapyramidal Symptoms; FBR=future biomedical research; FSH=follicle-stimulating hormone; h=hour; HAM-D17=Hamilton Depression Rating Scale; hCG=human chorionic gonadotropin; IC=inclusion criteria; ID=identification; PGA=planned genetic analysis; POCBP=participant of childbearing potential; PONCBP=participant of nonchildbearing potential; SAS = Simpson-Angus Scale; SAE=serious adverse event; SOP=standard operating procedure; VS=vital signs; YMRS=Young Mania Rating Scale.

- a Rescreening is defined as a separate screening period. All activities conducted during Screening must be completed as part of Rescreening. See Section 8.10.1.
- b Meals should be given at approximately the same time on the days specified in the SoA. Breakfast will be given at ~ 1-hour postdose, lunch given at ~ 4-hours postdose, a snack given at ~ 8-hours postdose and dinner at ~ 12-hours postdose. All meals will follow the completion of all specified procedures at that timepoint.
- c Participants currently treated with antipsychotic therapy will be domiciled from Day -5 prior to Day 1 (to start washout period) and will remain in the CRU until 72 hours post the last dose on Day 14. Participants not currently being treated with antipsychotic therapy may be domiciled minimally starting on Day -1 through 72 hours post the last dose on Day 14. Participants may stay longer at PIs discretion.
- d In the event the urine pregnancy test is positive or cannot be confirmed negative, a serum pregnancy test will be required.
- e Additional assessment may be performed at the discretion of the investigator.
- f PK sampling timepoints are below for all Panels.  
Day 1: Predose and 2, 6, 8, 10, 12, 16, 24 (Day 2) hours postdose  
Day 8: Predose and 2, 6, 8, 10, 12, 16, 24 (Day 9) hours postdose  
Day 14: Predose and 8, 12, 24 (Day 15), 36 (Day15), 48 (Day 16), 72 (Day 17) hours postdose

## 2 INTRODUCTION

### 2.1 Study Rationale

MK-8189 is currently being evaluated in a Phase 2b study for the treatment of adults with Schizophrenia. A signal for efficacy was previously observed in a Phase 2 POC study (P005) where participants were titrated from 4 mg QD of MK-8189 to 12 mg QD of MK-8189. The Phase 2b study is currently evaluating safety and efficacy of MK-8189 when participants are titrated from 4 mg to 16 mg or 8 mg up to 24 mg QD. As there is substantial precedent for therapies effective in the treatment of schizophrenia to also be effective in the treatment of bipolar I disorder (i.e., olanzapine, risperidone, aripiprazole, quetiapine and cariprazine), MK-8189 will also be evaluated for the treatment of bipolar I disorder. Furthermore, the target dose range for these indications is usually the same for both indications and in some cases the starting dose may be higher for bipolar I disorder. A previous study (P011, Part 1) demonstrated that initiating dosing at the highest clinical dose in adult participants with schizophrenia was generally well tolerated, suggesting titration is not necessary for good tolerability. As there is an expected benefit to reaching the target clinical dose as quickly as possible during a manic episode, this study will also evaluate a starting dose of 24 mg QD, the highest clinical dose, in participants with bipolar I disorder. These data in conjunction with the Phase 2b data in schizophrenia participants will be used to support dose selection for Phase 3 trials.

### 2.2 Background

Refer to the IB for detailed background information on MK-8189.

#### 2.2.1 Pharmaceutical and Therapeutic Background

MK-8189 is a small molecule inhibitor of the PDE10A enzyme that is being developed for the treatment of schizophrenia and bipolar disorder. PDE10A is a member of the cyclic nucleotide phosphodiesterase family that functions to metabolically inactivate both cAMP and cGMP. PDE10A is highly expressed in the brain and has limited expression in peripheral tissues; in the brain, PDE10A is expressed at high levels in the medium spiny neurons of the striatum. Functional imaging studies have revealed that bipolar disorder is associated with exaggerated dopamine signaling in the striatum, consistent with schizophrenia, suggesting that striatal dysfunction may be a common neurobiology underlying psychosis [Karcher, N. R., et al 2019]. Preclinical studies have generated substantial evidence to support the hypothesis that PDE10A inhibition is a novel therapeutic target that regulates striatal activity. In vitro and in vivo assays demonstrate that PDE10A inhibition activates the Dopamine D2 receptor indirect pathway, similar to current antipsychotic medications, while also facilitating D1 receptor direct pathway and glutamatergic signaling in the striatum. PDE10A-deficient mice show reduced exploratory behavior when placed in a novel environment and have a blunted response to the psychomotor activating effects of NMDA receptor antagonists, phencyclidine and MK-801. In addition, administration of selective PDE10A inhibitors decrease psychomotor activity, reverse deficits in prepulse inhibition, and inhibit conditioned avoidance responding in rodents, models that are predictive of antipsychotic activity in the clinic. PDE10A inhibitors are also efficacious in nonclinical assays that test cognitive

domains impaired in psychiatric disorders, models of negative symptoms and decrease body weight in diet-induced obese animals. As described in Section 2.1, a signal for efficacy in participants with schizophrenia has been observed and based on precedent with many other antipsychotics, it is expected that efficacy would also be expected in participants with bipolar I disorder.

Bipolar disorder is a chronic lifetime condition affecting 1-4% of the population globally. Bipolar I Disorder is characterized by the occurrence of at least one manic or mixed episode, interspersed with periods of full or partial remission. Second-generation anti-psychotics are indicated to treat acute manic or mixed features. Atypical antipsychotic monotherapy currently available are associated with tolerability issues e.g., weight gain, metabolic issues, EPS, sedation, and hyperprolactinemia that can lead to reduced treatment adherence or discontinuation of therapy. A recent meta-analysis estimated typical weight gain of 3.8 kg in drug-naïve patients after starting antipsychotic treatment in the first 3 months of treatment. Obese bipolar patients have a 10-year shorter life span due to the higher CVD risk and vascular age. As a result, there is still a significant unmet need in this patient population.

## 2.2.2 Preclinical and Clinical Studies

The nonclinical safety profile of MK-8189 was determined in a series of safety pharmacology studies, genetic toxicology studies, oral repeat-dose toxicity/tolerability studies in rats and rhesus non-human primates (NHPs), reproductive and developmental toxicity studies in rats and rabbits, and repeat-dose tolerability studies in wild-type TgRasH2 mice. The pivotal nonclinical safety assessment studies, conducted in compliance with Good Laboratory Practice (GLP), support the use of MK-8189 in patients of  $\geq 13$  years old.

Preclinical and clinical study information can be found in the MK-8189 IB.

Four single-dose clinical studies (P001, P002, P004, P010) in healthy participants, a single dose study in healthy participants and participants with moderate hepatic impairment (P012), 2 CYP3A DDI studies in healthy participants (P006, P015), and 4 multiple-dose clinical studies in healthy participants and participants with schizophrenia (P003, P007, P011, P016) have been completed with MK-8189. One multiple-dose study in participants with Alzheimer's disease has also been completed (P017). Protocol 011 included elderly ( $>60$  years of age, n=12) participants with schizophrenia and healthy elderly ( $> 60$  years of age, n=18) participants. Protocol 017 included 29 elderly participants ( $\geq 65$  years of age) with Alzheimer's disease. Please see IB for a summary of completed studies and Section 2.2.3 for a summary of ongoing studies.

Overall, across the completed studies, 259 participants have received at least one dose of MK-8189; 130 participants without schizophrenia, 107 participants with schizophrenia and 22 participants with Alzheimer's Disease.

Across completed and ongoing studies, MK-8189 was generally well tolerated up to 24 mg in healthy participants and up to 80 mg in participants with schizophrenia. The most common treatment-related AEs ( $\geq 5\%$ ) following treatment of MK-8189 (n=259) across the 12 completed Phase 1 studies which included, healthy participants (non-elderly and elderly),

### **2.3     Benefit/Risk Assessment**

It cannot be guaranteed that participants in clinical studies will directly benefit from treatment during participation, as clinical studies are designed to provide information about the safety and effectiveness of an investigational medicine.

Additional details regarding specific benefits and risks for participants participating in this clinical study may be found in the accompanying IB and informed consent documents.

### 3 HYPOTHESES, OBJECTIVES, AND ENDPOINTS

Hypotheses are aligned with objectives in the Objectives and Endpoints table.

The following objectives will be evaluated in male and female participants with bipolar I disorder:

Primary Objective	Primary Endpoint
To evaluate the safety and tolerability of multiple doses of MK-8189 in participants with bipolar I disorder, manic or mixed features	Adverse events Adverse experiences leading to discontinuation of study intervention
Secondary Objectives	Secondary Endpoints
Not applicable	Not applicable
Tertiary/Exploratory Objectives	Tertiary/Exploratory Endpoints
To evaluate the PK profile of MK-8189 in participants	Cmax, AUC0-24, Tmax, t1/2, C24, Vz/F, CL/F
To evaluate the safety and tolerability of multiple doses of MK-8189	VS, ECG, Laboratory safety values, C-SSRS, BARS, SAS, AIMS, CGI-BP-S, YMRS, HAM-D17
Objective: To explore the relationship between genetic variation and response to the treatment(s) administered, and mechanisms of disease. Variation across the human genome may be analyzed for association with clinical data collected in the study	Germline genetic variation and association to clinical data collected in this study

## 4 STUDY DESIGN

### 4.1 Overall Design

This is a randomized, double-blind, placebo-controlled, multiple dose study to evaluate the safety and tolerability of MK-8189 in participants with stable bipolar I disorder. The study will evaluate up to 3 dose regimens within 3 Panels (Panels A, B and C). The intent will be for ~16 participants to complete at least one of the 3 specified dose regimens.

Panel A will enroll an initial cohort of 8 participants and receive 24 mg MK-8189 QD (2 x 12 mg tablet) for 14 days (Dose Regimen 1) or placebo (3:1). If Dose Regimen 1/placebo is generally well tolerated based on AE reporting, an additional 8 participants will be enrolled to receive Dose Regimen 1/placebo and the decision to also enroll Panel B or Panel C in parallel with Panel A will be determined to further explore optimal tolerability. If Dose Regimen 1/placebo is not considered to be generally well tolerated following the initial 8 participants, then 8 participants will be enrolled in Panel B or Panel C.

Panel B will receive 16 mg MK-8189 (1 x 12 mg tablet and 1 x 4 mg tablet) QD Days 1 to 3 and 24 mg MK-8189 (2 x 12 mg tablets) QD Days 4 to 14 (Dose Regimen 2) or placebo (3:1). If Dose Regimen 2/placebo is generally well tolerated based on AE reporting, an additional 8 participants will receive Dose Regimen 2/placebo in Panel B and the decision to also enroll Panel C in parallel with Panel B will be determined. If Dose Regimen 2/placebo is not well tolerated, an initial cohort of 8 participants will be enrolled in Panel C.

Panel C will receive 8 mg MK-8189 (2 x 4 mg) Day 1, 16 mg MK-8189 (1 x 12 mg tablet and 1 x 4 mg tablet) Day 2 and 24 mg MK-8189 (2 x 12 mg tablet) QD Days 3 to 14 (Dose Regimen 3) or placebo (3:1). If Dose Regimen 3/placebo is generally well tolerated based on AE reporting, an additional 8 participants will be enrolled in Panel C. If Dose Regimen 3/placebo is not well tolerated, no additional participants will be enrolled in Panel C and an alternate more conservative regimen may be evaluated per Section 8.10.6.

[figure not shown]
In Panels A, B and C, participants randomized to placebo will receive the same number of tablets matching the MK-8189 tablet strengths in the active group. See Study Design Diagram ([Figure 2](#)) below for the dose regimen decision tree.

If applicable, participants will be washed off their current antipsychotic therapy. The washout may start with a down titration of the antipsychotic treatment during the screening phase per direction of the investigator. Participants should not receive antipsychotics for at least 5 days or 3 half-lives (whichever is longer) prior to Day 1. For longer half-life antipsychotics (eg, aripiprazole and brexpiprazole), if deemed appropriate by the investigator, a participant may stop treatment (ie, cessation of atypical antipsychotic therapy) as an outpatient, but should be confined to the clinical research unit within a week of stopping treatment and minimally beginning on Day -5. Antipsychotic SOC may be restarted following the assessments that occur 72-hours following the last dose of study drug. At the investigator's discretion, the participant may be domiciled for a longer duration i.e., participants may be domiciled prior to Day -5 or for a longer period following end of study treatment while SOC is restarted.

Where applicable (Dose Regimen 2 or 3), titration to the next dose level within a regimen will occur per the investigator's medical discretion based on the tolerability of study intervention within an individual participant. If the investigator deems it necessary, dose titration within an individual may be paused temporarily for the duration of any tolerability issues (i.e., AEs) and resumed when deemed appropriate. Any changes to the dose regimen will not prolong an individual's participation in the trial and therefore it is acknowledged that failure to adhere to the protocol-defined dose regimen may result in some participants not reaching the escalation targets. Participants may be down-titrated by the investigator at any time without consultation of the Sponsor in the case of safety or tolerability issues.

Regardless of the state of the dose escalation of each participant it is important to keep participants in the study as the data collected at all doses is valuable for the purposes of defining a clinical tolerability margin. Any changes to the protocol specified treatment regimen will be documented in a Protocol Clarification Letter.

Figure 2 Study Design Diagram

Following completion of 14 days of dosing in at least 6 participants, a decision to enroll an additional 8 participants in the current panel and enroll participants in a more conservative dose regimen (per [Figure 2](#)) will be made jointly by the investigator(s) and Sponsor. Dose regimen decisions will be based on the review of adverse event data. The Dose Regimen selected will be documented in a Protocol Clarification Letter.

Because this is a Phase 1 assessment of MK-8189 in humans, the PK, pharmacodynamic, and safety profiles of the compound are still being elucidated. This protocol is therefore written with flexibility to accommodate the inherent dynamic nature of Phase 1 clinical studies.

Refer to Section 8.10.6 for examples of modifications permitted within the protocol parameters.

Specific procedures to be performed during the study, including prescribed times and associated visit windows, are outlined in Section 1.3 of the SoA. Details of each procedure are provided in Section 8.

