### **8.4.1 Time Period and Frequency for Collecting AE, SAE, and Other Reportable Safety Event Information**

AEs, SAEs, and other reportable safety events that occur after the participant provides documented informed consent, but before intervention allocation, must be reported by the investigator under any of the following circumstances:

- if the participant is receiving placebo run-in or other run-in treatment,
- if the event causes the participant to be excluded from the study,
- if it is the result of a protocol-specified intervention, including, but not limited to washout or discontinuation of usual therapy, diet, placebo, or a procedure.

From the time of intervention allocation through 14 days after cessation of intervention, all AEs, SAEs, and other reportable safety events must be reported by the investigator.

Additionally, any SAE brought to the attention of an investigator any time outside the period specified in the previous paragraph also must be reported immediately to the Sponsor if the event is considered related to study intervention.

Investigators are not obligated to actively seek AEs or SAEs or other reportable safety events in former study participants. However, if the investigator learns of any SAE, including a death, at any time after a participant has been discharged from the study, and the investigator considers the event to be reasonably related to the study intervention or study participation, the investigator must promptly notify the Sponsor.

All initial and follow-up AEs, SAEs, and other reportable safety events will be recorded and reported to the Sponsor or designee within the time frames as indicated in [Table 3](#).

Exception: A positive pregnancy test at the time of initial screening is not a reportable event unless the participant has received study intervention.

Table 3 Reporting Periods and Time Frames for Adverse Events and Other Reportable Safety Events

Type of Event	Reporting Period: Consent to Randomization/ Allocation	Reporting Period: Randomization/ Allocation through Protocol-specified Follow-up Period	Reporting Period: After the Protocol-specified Follow-up Period	Time Frame to Report Event and Follow-up Information to Sponsor
NSAE	Report if: – due to protocol-specified intervention – causes exclusion – participant is receiving placebo run-in or other run-in treatment	Report all	Not required	Per data entry guidelines

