### **8.10.2 Treatment Period Visit**

Refer to the Schedule of Activities (Section 1.3).

Participants must be washed out from any antipsychotic therapy for at least 5 days or cover at least 3 half-lives of the drug (whichever is longer) prior to Day 1. Participants will report to the CRU on Day -5 to start their washout period. However, if participants are not currently being treated with antipsychotic medications and therefore do not require a washout, they may be domiciled on Day -1.

On treatment days, participants will be dosed once daily with MK-8189 or placebo and have procedures completed per the SoA. Participants will remain in the unit through 72 hours post the last dose and completion of all procedures and will be discharged at the discretion of the investigator.

Participants will resume the use of their own antipsychotic medication after the completion of the last PK sample collection (72 hr postdose).

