### 9.3 Analysis Endpoints

#### 9.3.1 Primary Endpoints

Safety:

Clinical assessment of AEs and participant discontinuation due to AEs.

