### **9.5.2 Statistical Methods for Safety Analyses**

Primary:

Safety and tolerability will be assessed by clinical review of AEs.

The overall safety endpoints include the number of participants with at least one AE, drug-related AE, serious AE, serious, drug-related AE, who discontinue from study intervention due to an AE, or with an AE resulting in death.

The safety evaluation will include a summary by treatment group of the number and percentage of participants with each type of AE.

Exploratory:

Safety and tolerability will also be assessed by clinical review of other relevant parameters, including laboratory test results, vital signs, and ECG measurements.

Summary statistics and plots will be generated for raw laboratory safety tests, ECGs, and vital signs as well as for change from baseline by treatment group, as deemed clinically appropriate. Depending on the safety parameter, the difference from baseline will either be computed on the original scale (raw change from baseline) or on the log scale and back-transformed for reporting (percent change from baseline).

To explore changes in extrapyramidal symptomology, summary statistics will be generated for BARS, AIMS, SAS as well as for change from baseline. The difference from baseline will be computed on the original scale (raw change from baseline). Responses to the C-SSRS will be listed. The C-SSRS will be used to systematically and prospectively ascertain and document the occurrence of suicidal events (i.e., ideation and behavior). Summary statistics for changes in baseline for CGI-BP-S will be provided.

Changes from baseline in YMRS total scores, HAM D17 total scores, and HAM D6 will be summarized. The 6-item HAM D6 is a subset of the HAM D17. It consists of 6 items (depressed mood, work and activities, somatic symptoms general, feelings of guilt, anxiety psychic, and retardation); these items are summed to obtain the HAM-D6 total score.

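### Section 9.5.2 sets no onset window for the primary AE table, so AEs that start after a participant resumes an antipsychotic count under MK-8189 or placebo

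*Combined protocol and SAP*

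**What the plan says.** The primary endpoint in Section 9.3.1 is "Clinical assessment of AEs and participant discontinuation due to AEs".

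**Collection.** Section 8.4.1 sets the reporting period: "From the time of intervention allocation through 14 days after cessation of intervention, all AEs, SAEs, and other reportable safety events must be reported". The synopsis agrees: "After the end of treatment each participant will be followed for 14 days".

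**Restart of antipsychotics.** Section 4.1 is permissive: "Antipsychotic SOC may be restarted following the assessments that occur 72-hours following the last dose of study drug". The washout text in Section 8.1.5.1 is permissive too. Section 8.10.2 is firm: "Participants will resume the use of their own antipsychotic medication after the completion of the last PK sample collection (72 hr postdose".

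**Analysis.** Section 9.5.2 states: "The safety evaluation will include a summary by treatment group of the number and percentage of participants with each type of AE". The population is everyone who received at least one dose (Section 9.4.1), grouped by the treatment actually received (Section 9.4). Sections 9.3 to 9.5 contain no treatment-emergent definition, no onset window, no division into treatment and follow-up phases, and no cut at antipsychotic restart.

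**Data available.** Start and stop times of concomitant medications are recorded (Section 8.1.5.2).

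**The concern.** Section 2.2.1 lists EPS and sedation among the tolerability problems of available antipsychotics. Sections 4.2 and 6.6 name EPS as an acute tolerability concern for MK-8189. The event that could come from the restarted drug is therefore of the same kind as the event the study is watching for.

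Take a participant who finishes dosing on Day 14, resumes an antipsychotic on Day 17 and has a dystonia that starts on Day 20. Under Section 9.5.2 as written, that event is a dystonia under MK-8189, or under placebo. The EPS scales are last scheduled on Day 14 (Section 1.3), so later EPS would enter mainly through AE reporting, which is the part of the analysis with no window.

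Section 2.1 says the data will help to support dose selection for Phase 3. What is at stake is the reading of the final AE percentages in very small groups.

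**Working it through.** **1. Reproduce the plan's own figures.** Duration of participation: screening up to 42 days, treatment about 14 days, follow-up 14 days. (42 + 14 + 14)/7 = 10.0 weeks, which matches the synopsis. Total size: 3 panels × (12 + 4) = 48, which also matches.

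**2. Length of the overlap, for a participant who takes all 14 doses.**
- Last dose: Day 14 (Section 1.3).
- Earliest restart under the 72-hour rule: 14 + 3 = Day 17.
- End of AE reporting: 14 + 14 = Day 28.
- Days after the earliest restart: 28 − 17 = 11.
- Share of the 28-day window: 11/28 = 39%. Share of the 14-day follow-up: 11/14 = 79%.

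This is an upper limit for completers. It is zero for those who take no antipsychotic, and Sections 8.1.11 and 8.10.2 show that some participants are on none at entry. It does not cover a participant who stops study drug early because an antipsychotic has to be added (Sections 6.5.1 and 6.6.1.2) and stays in follow-up under Section 7.1. That participant's exposure to the added drug can begin before the 72-hour point.

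**3. Weight of one participant (Section 9.8).** One participant whose only AE of a given type begins after restart moves that rate by 1/12 = 8.3 points on active or 1/4 = 25 points on placebo, within a panel.

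**4. Illustration. Every rate in this step is an assumption; none is in the documents.** Let a share f of participants restart, and let a share q of those have an AE attributable to the restarted drug before Day 28. The whole-group risk is r = f × q. With f from 50% to 100% and q from 10% to 30%, r runs from 0.05 to 0.30.

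| Per panel | r = 0.05 | r = 0.30 |
|---|---|---|
| Expected participants, active (12r) | 0.6 | 3.6 |
| Expected participants, placebo (4r) | 0.2 | 1.2 |
| Chance of at least one, active: 1 − (1 − r)^12 | 46% | 99% |
| Chance of at least one, placebo: 1 − (1 − r)^4 | 19% | 76% |

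For the any-AE count, suppose the risks up to restart are 60% on active and 30% on placebo, with the restart risk independent and equal in both groups. The tabulated risk is 1 − (1 − p)(1 − r).
- r = 0.10: 1 − 0.4 × 0.9 = 64% and 1 − 0.7 × 0.9 = 37%, a gap of 27 points instead of 30.
- r = 0.30: 1 − 0.4 × 0.7 = 72% and 1 − 0.7 × 0.7 = 51%, a gap of 21 points.

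Under these assumptions both rates rise and the descriptive gap narrows by the factor 1 − r.

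**The case against.** The case on the other side is substantial, and most of it limits the size of the point.

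- **A reader might infer that the SAP defines the AE summary to run to 14 days after the last dose.** It does not. Section 8.4.1 is a reporting period and Section 9.5.2 is silent. The defect is that no window is prespecified, so the collection period applies by default.
- **A reader might infer that the choice of regimen within the study is distorted.** The documents do not support that. Regimen decisions rest on acute tolerability after 14 days of dosing (Sections 4.1 and 6.6). The regimens differ only on Days 1 to 3, so restart from Day 17 has no built-in tendency to favour one of them.
- **Other endpoints are largely protected.** AEs leading to discontinuation of study intervention arise while dosing continues. The EPS scales end on Day 14. The drug-related AE counts pass through a causality assessment that considers other drugs (Section 10.3.5). That filter is imperfect for EPS, because the same assessment asks whether the event fits the study drug's known profile. It does not apply to the table of each AE type.
- **A reader might claim a known loss in the active–placebo contrast.** No formal contrast or hypothesis is planned (Sections 9.5.2 and 9.7), and the rates in the illustration are assumed. Those who resume take their own drug, have a history of tolerating antipsychotics (inclusion criterion 2) and have had no recent psychotropic change (inclusion criterion 1). Their rate of new EPS may be low.
- **A reader might want to end the main table at 72 hours for everyone.** That would move late AEs of participants who never restart, where no such confounding exists, out of the main table. A cut at the recorded restart deals with the stated problem without that loss.

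What stands against all this is that the all-causality table of the primary endpoint has no rule for AEs that begin on another antipsychotic.

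**Conclusion.** The point holds as a gap in specification with a practical consequence. On a plain reading of Sections 8.4.1, 9.4 and 9.5.2, AEs that start after a participant resumes or adds an antipsychotic are tabulated under MK-8189 or placebo. Among completers who restart, up to 39% of the AE window is affected, and a single participant can shift a panel's rate by 8.3 points on active or 25 points on placebo.

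The direction, with both rates raised and the gap narrowed, follows if restart AEs are about equally likely in the two groups. The size cannot be fixed from the documents, because the share restarting and their AE rate are not given. The harm falls on the final descriptive AE rates and their use in planning Phase 3, not on the conduct of the study. The 14-day follow-up is not itself an error.

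**What to change.** In Section 9.5.2, before unblinding:

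1. Keep the all-AE summary over the full collection period, and state that period.
2. Add, as the main table for interpreting MK-8189 tolerability, AEs with onset from the first dose of study drug to the first dose of any restarted or added antipsychotic, or to the end of follow-up if none is taken. This rule also handles participants who stop early because an antipsychotic is added.
3. Tabulate AEs with onset after that point separately, by treatment group, among participants who took an antipsychotic. Give the number restarting and the days observed in each window, since the windows will differ in length.

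Sections 4.1 and 8.1.5.1 (*may* restart) and Section 8.10.2 (*will* resume) should be reconciled. Which wording is right is for the sponsor to settle.

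**Cost.** SAP wording and one or two extra tables. Collection, visits and patient management do not change, and AE onset and medication start times are already recorded. The price is that late effects of MK-8189 in participants who restart appear in the post-restart and all-AE tables rather than in the main one.
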